1. STATEMENT OF COMPLIANCE

The trial will be conducted in accordance with the International Conference on Harmonisation Good Clinical Practice (ICH GCP), and applicable United States (US) Code of Federal Regulations (CFR). The Principal Investigator will assure that no deviation from, or changes to the protocol will take place without prior agreement from the documented approval from the Institutional Review Board (IRB), except where necessary to eliminate an immediate hazard(s) to the trial participants. All personnel involved in the conduct of this study have completed Human Subjects Protection and ICH GCP Training.

The protocol, informed consent form(s), recruitment materials, and all participant materials will be submitted to the IRB for review and approval. Approval of both the protocol and the consent form must be obtained before any participant is enrolled. Any amendment to the protocol will require review and approval by the IRB before the changes are implemented to the study. All changes to the consent form will be IRB approved; a determination will be made regarding whether a new consent needs to be obtained from participants who provided consent, using a previously approved consent form.

1 PROTOCOL SUMMARY

1.1 SYNOPSIS

Title:	Clinical effectiveness of pre-incision versus post-incision local anesthetic during laparoscopic/robotic sacrocolpopexy
Study Description:	To compare postoperative narcotic use and pain score with pre-incisional versus post-incisional injection of local anesthetic at trocar sites in robotic/laparoscopic-assisted sacrocolpopexy
Objectives:	
Primary objective: Comparing postoperative Likert pain scale between patients who received pre-incisional versus post-incisional local anesthetic on postoperative day oneSecondary objectives: Total narcotic use over two weeks between patients who received pre-incisional versus post-incisional local anesthetic. To compare the pain levels reported by patients on the brief pain inventory questionnaire at POD14 between the two study groups (pre-incisional vs post-incisional) by two sample t –test or Wilcoxon rank-sum test, where appropriate.

Endpoints:	Primary Endpoint: comparing Likert-pain scale scores between pre-incisional versus post-incisional local anesthetic on postoperative day one Secondary Endpoints: total narcotic use over two weeks between patients who received pre-incisional versus post-incisional local anesthetic and to compare brief pain inventory questionnaires at POD14 between the two study groups.
Study Population:	Sample size – 64 per arm; Female gender, age \geq 18 years old, general health status healthy
Phase:	N/A
Description of Sites/Facilities	Northwell Health sites (Lenox Hill Hospital, Southshore Hospital, Long Island Jewish Hospital, Northshore Hospital, Huntington Hospital, Plainview, Peconic, Mather). No hospital outside of the US.
Enrolling Participants:	Subcutaneous injection of 4-5mL of 0.25% Bupivacaine into skin before or after incision for trocar placement during robotic/laparoscopic- assisted sacrocolpopexy
Description of Study Intervention:	
Study Duration:	18 months
Participant Duration:	2 weeks

1.2 SCHEMA

Visit 0

- New patient/Surgical discussion Visit
 - Screen potential for inclusion and exclusion criteria
 - If meets criteria
 - Pamphlet provided to patient in regard to study information

Visit 1

- Preoperative visit
 - Discuss study in further detail, answer questions after patient read pamphlet, risks/benefits discussed and offer patient participation
 - If patient consents:
 - First Brief Pain Inventory Questionnaire to fill out prior to surgery. The Narcotic Diary will be given to patient with the instructions to fill out after surgery and to document all narcotic pills used including provided and any additional.
 - If a patient is undecided, then will follow up by phone call prior to surgical day. If she decides after follow up phone call then will have patient sign consent on day of surgery

Visit 2

- Day of surgery

- If patient does not consent at preoperative visit, but decides to participate after follow up phone call:
 - Obtain consent if patient has agreed by phone call (phone call which is after preoperative visit) on the day of surgery
 - Provide narcotic diary and first Brief Pain Inventory Questionnaire to fill out (if patient has not already filled it out previously). Patient only needs to fill out one brief pain inventory questionnaire prior to surgery, the patient should fill this out on the day that they sign the consent for participation (whether it is at the preoperative visit or in the preoperative suite on the day of surgery). The Narcotic Diary will be given to patient with the instructions to fill out after surgery and to document all narcotic pills used including provided and any additional.
- Randomization
 - Arm 1: 64 patients; Arm 2: 64 patients

Visit 3

- Postoperative Day 1
 - Obtain Likert-pain scale score between 18-24 hours post-surgery

Visit 4

- Postoperative Visit (14 days +/- 3 days)
 - Narcotic Diary collected
 - Second Brief Pain Inventory Questionnaire given to patient to complete

1.3 SCHEDULE OF ACTIVITIES (SoA)

Procedures	Screening Visit (Visit 0)	Preoperative Visit (Visit 1)	Day of Surgery (Visit 2)	Postoperative Day#1 (Visit 3)	Final Study Visit Day 14 +/-3 day (Visit 4)
Informed consent		X			
Demographics	X	X			
Medical history	X	X			
Randomization			X		
Administer study intervention			X		
Concomitant medication review	X	X		X	X

Physical exam (including height and weight)*	X	X			X
Vital signs*	X	X	X	x	X
Height*	X	x			
Weight*	X	x	X		
Hematology*		X		X	
Serum chemistry*		X			
Pregnancy Test*			X		
EKG (as indicated)*		X			
Adverse event review and evaluation		X	X-----X		X
Radiologic/Imaging assessment*		X			X
Other assessments (e.g., immunology assays, pharmacokinetic)*		X	X	X	X
Complete Case Report Forms (CRFs)		X	X	X	X
Brief Pain Inventory Questionnaire **		x	x		x

*Results of these standard of care procedures (if available) will be collected for research purposes via medical record review

**Patient will fill out this only one time prior to surgery on the day she consents to participate in the clinical trial.

2 INTRODUCTION

2.1 STUDY RATIONALE

Pelvic organ prolapse is becoming more common as women's life expectancy is increasing and the prevalence of obesity is rising. Many women undergo pelvic reconstructive surgery to treat their prolapse and improve their quality of life. The incidence of pelvic organ prolapse is 1.5-1.8 surgeries per 1,000 women years (1). Approximately 300,000 pelvic reconstructive surgeries are performed each year in the United States (1). There is a wide variety in surgical approaches and procedures for prolapse. One such procedure is a sacrocolpopexy in which the cervix or vaginal cuff is lifted to the anterior longitudinal ligament overlying the sacrum via a mesh graft. This can be done in a minimally invasive fashion with a laparoscopic or robotic approach or in an open abdominal approach. Numerous studies have shown this procedure to have a high success rate and long-term durability (2). As robotic/laparoscopic approach to surgery has shown shorter hospital-stays and improved patient outcomes, the robotic-assisted sacrocolpopexy has been rapidly incorporated into clinical practice (2).

In general, surgery causes a release of painful chemical mediators which has led to increased narcotic use, increased narcotic addiction, and number of pills prescribed. Most individuals who undergo surgery will require narcotics postoperatively to control their pain and some individuals have to extend their hospital stay until adequate pain control is achieved. Our study is aimed to reduce narcotic use, decrease hospital stay due to pain issues and determine if timing of adjunct pain medication improves pain scales for patients.

As postoperative pain after minimally invasive surgery is complex, specialists suggest that the effective analgesic treatment should be a multimodal approach (4). Use of local anesthetic with bupivacaine at robotic/laparoscopic trocar sites is the standard of care, however, there is no standard as to optimal timing that is most beneficial for patients to decrease pain. Currently, bupivacaine is used by providers at the trocar sites at either the beginning of the case or at the end of the case. From clinical

observation, it appears that postoperative pain levels reported from patients receiving either at the beginning of surgery (pre-) or end (post-incision) of the surgery are similar. This study aims to examine the difference in POD1 pain levels reported by patients between the two infiltration methods.

2.2 BACKGROUND

Subcutaneous infiltration with bupivacaine at robotic/laparoscopic port sites is standard of care. It is currently injected into incision sites during laparoscopic or robotic trocar sites before or after the incision is made. However, there is no standard as to which time during the procedure is the most beneficial for patients in order to decrease pain. Currently, there is lack of studies in the current literature that describe pre-incisional vs post-incisional local infiltration of numbing medication during robotic/laparoscopic-assisted sacrocolpopexy. There have been similar studies for patients undergoing laparoscopic cholecystectomy in which timing of the Marcaine was given to one group prior to incision and in another group at the end of the procedure, however in this study there was no difference in the pain scores at various times evaluates postoperatively. Our study is aimed to determine if the timing of local infiltration improves pain scales during robotic/laparoscopic sacrocolpopexy, which is a considerably longer procedure (approximately 3-5 hours). There is currently no literature on comparing Likert-pain scale scores in patients during robotic/laparoscopic sacrocolpopexy.

2.3 RISK/BENEFIT ASSESSMENT

2.3.1 KNOWN POTENTIAL RISKS

Bupivacaine (brand name: Marcaine)

- Immediate common risks: edema at insertion site, seroma
- Long-range common risks: hypersensitivity reaction, hypotension, localized numbness, cardiac arrest, methemoglobinemia and dose related toxicity
- Injection of Marcaine at skin incision sites will be lower than the dose that causes potential risks

This research will collect subject's personal health information, and there is a risk of breach of confidentiality.

Some of the questions on the questionnaires are personal and subjects may feel embarrassed or stressed.

Since subjects will be randomized to one of the two groups, some may receive less effective treatment and/or have more side effects than those in the other group.

2.3.2 KNOWN POTENTIAL BENEFITS

Subjects will be randomized, and some may experience less pain and/or fewer side effects than those in the other group.

2.3.3 ASSESSMENT OF POTENTIAL RISKS AND BENEFITS

- Local infiltration of incision sites with bupivacaine is standard of care for surgery.
- Adverse short term and long term risks: we will be using a standard dose that is currently used in the operating suite, which is lower than what would cause adverse side effects

3 OBJECTIVES AND ENDPOINTS

OBJECTIVES	ENDPOINTS	JUSTIFICATION FOR ENDPOINTS
Primary Difference in Likert-pain scale score difference between pre-incision versus post-incision subcutaneous infiltration with 4-5mL 0.25% Bupivacaine at 18-24 hours postoperatively	Likert-pain scale score difference between pre-incision and post-incision subcutaneous infiltration at 18-24 hours postoperatively.	To determine if timing of local anesthetic affects postoperative pain scores.
Secondary To compare total narcotic usage over two weeks	Total number of narcotic tablets used in the first two weeks postoperatively between pre-incision and post-incision subcutaneous infiltration with 4-5mL 0.25% Bupivacaine	To decrease postoperative narcotic usage
Secondary Compare brief pain inventory questionnaire survey score	To compare score levels of the brief pain inventory questionnaire at POD14 between the two study groups	To decrease pain score for patient post surgery

4 STUDY DESIGN

4.1 OVERALL DESIGN

- Central Objective To examine patients reported pain levels or narcotic usage between pre-incision versus post-incision subcutaneous infiltration of 4-5mL 0.25% Bupivacaine after a robotic/laparoscopic-assisted sacrocolpopexy.

Research Plan:

- Randomized, controlled, single-blinded study

Setting of the study:

- Operating room of patients undergoing robotic/laparoscopic sacrocolpopexy

Participants:

- Patients aged 18 years old and above who are scheduled to undergo robotic/laparoscopic-assisted sacrocolpopexy (with or without hysterectomy and with or without midurethral sling)

Randomization Scheme

- Randomization will be accomplished using the Biostatistics Randomization Management System
- 1:1 Randomization, permuted blocks
- Subjects will be randomized using a computer generated table into one of two groups:
 - Arm one: subcutaneous infiltration pre-incision
 - Arm two: subcutaneous infiltration post-incision
- Surgeons will be notified by e-mail of their patient allocation on day of surgery

Pre-surgery

- Consent will be obtained and the patient will be given a Brief Pain Inventory Questionnaire to complete. The Brief Pain Inventory Questionnaire is a validated medical questionnaire to measure pain. The questionnaire measures the patient's pain intensity and the amount of interference the pain has on their being able to function in their daily living.
- Intervention or experimental aspect of the study
 - General anesthesia will be given as per standard protocol
 - Preoperative pain medication will be ordered for each patient as per standard enhanced recovery protocol
 - Operative Time: Generally total of 180 – 300 minutes
 - Total dose of 0.25% Bupivacaine injection:
 - 8-10 mm incisions x 5 incisions = 20-25 mL (4-5 mL each)
 - 20-25mL of 0.25% Bupivacaine distributed over 5 trocar sites (4-5mL per incision)
 - Skin closure: subcutaneous closure with monofilament absorbable suture with 4-0 absorbable suture and fascia closure of the umbilical port site with #0 delayed absorbable suture and skin closure with 4-0 absorbable suture

- Pre-incision arm: Marcaine (bupivacaine) injected in the umbilical port site subcutaneously, while in the other 4 sites injection under direct visualization
- Post-incision arm: local anesthetic infiltrated subcutaneously at the end of the procedure after trocar removal and after skin closure with suture
 - Postoperative pain medication will be ordered for each patient as per standard enhanced recovery protocol
 - On Postoperative Day 1, the patient will be asked her pain scale on the Likert-pain scale. The Likert-pain scale is a 0-10 discrete integer scale. The investigators will check for patient's pain medication use before questionnaire administration. If a patient has received postoperative pain medication, the questionnaire will be administered at least 1.5 hours after the patient has received the pain medication.
 - Discharge medications will be ordered for each patient as per standard enhanced recovery protocol
 - The Brief Pain Inventory Questionnaire will be given to the patient at the 2 -week postoperative visit to be filled out and collected at the postoperative visit.
 - The Narcotic diary (in which the patient writes down how many narcotic tablets they have used per day since the surgery (provided and additional included) will be collected at the postoperative visit.

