9.2 SAMPLE SIZE DETERMINATION

We used pain score measured at POD1 as our primary outcome of interest. Sample size calculation was calculated using two independent sample t test, under the assumption that the pain scores are normally distributed. At the following test settings:

H_{null} : Mean difference of pain levels reported on a Likert-pain scale by patients between pre- and post-incision arms at POD1 = 0;

H_a : Mean difference of pain levels reported on a Likert-pain scale by patients pre- and post- incision arms at postoperative day one $\neq 0$, and the expected mean difference of pain levels between the two groups is 1 likert point*.

Further we assume,

Standard deviation (std) = 2;

With the following default set-up values:

Alpha = 0.05

Power = 0.8

Weight between study arms = 1 (equal sample size in each arm)

Drop-out rate = 0

The required sample size for the current study is **64 per arm or 128 in total**.

*No well-established mean difference between the two study groups can be found in the literature. Based on clinical observations and experience from physicians that the two different infiltration methods are currently used interchangeably with no obvious difference in patients reported POD1 pain, we hypothesize the likely difference of pain levels between the two study groups to be 1. With standard deviation of 2 (see below), our targeted effect size is 0.5, or a median size effect based on Cohen's rule (Cohen, 1989).

**This SD value was estimated from the study by Yeung et al. (Liposomal Bupivacaine During Robotic Colpopexy VOL. 131, NO. 1, JANUARY 2018) using data from Table 3, average pain with rest at POD1 for the Bupivacaine group. Yeung et al. showed that the mean pain level with rest at POD1 in patients treated with liposomal Bupivacaine was 18.0, with the range of data being 81, on a 100mm-VAS scale. Therefore, a 'rule-of-thumb' of estimating standard deviation: range of data/4 was taken, yielding sd of ~20mm on a VAS scale. This was further translated to a sd of 2 on a 10-point Likert scale as one of the parameters for the sample size calculation for the current study.

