9.4.2 ANALYSIS OF THE PRIMARY EFFICACY ENDPOINT(S)

Analysis of the primary outcome: For the primary outcome, which we assume will be normally distributed, the two independent sample t test comparing two independent groups will be used to compare the pain scores from study arms at POD1. In the event that normal assumption does not hold, a suitable data transformation (e.g., arcsine square-root, logit) will be applied.

A 95%, two-tailed confidence interval for the difference of mean pain scores between the two arms will be constructed. If both upper and lower confidence intervals lay within the ± 1 -unit margin, we will conclude that the pain scores associated with the two routes of wound infiltration are equivalent. Otherwise, we cannot conclude that the effects between the two modes of wound infiltration on postoperative pain are equivalent.

As per ICH E-9 guidelines, a supporting analysis will be conducted whereby analysis of covariance (ANCOVA) will be used to compare the two groups, adjusting for nuisance covariates.

All continuous secondary outcomes will be analyzed using two sample t-test or Mann-Whitney test depending on whether normal assumption holds or not. ANCOVA will be used adjusting for baseline values and other associated covariates and will be considered as supportive analysis.

All categorical secondary outcomes will be analyzed using chi-square test for proportions or Fisher's exact test, as appropriate.

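### The narcotic endpoint is a diary count of tablets with conflicting definitions, and no analysis compares opioid use between arms up to the POD1 pain score

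*Combined protocol and SAP*

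**What the plan says.** **The narcotic endpoint.** The Synopsis (1.1) gives the objective as "Total narcotic use over two weeks between patients who received pre-incisional versus post-incisional local anesthetic". Section 3 turns this into "Total number of narcotic tablets used in the first two weeks postoperatively". Section 4.1 takes the data from a diary recording "how many narcotic tablets they have used per day since the surgery", counting both the supplied tablets and any others; the Schema (1.2) likewise asks for pills.

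Sections 9.1 and 9.4.3 define the outcome differently, as the need for additional narcotic. Section 9.4.3 codes it yes/no, against a standard discharge supply of 12 pills, and compares it by chi-square or Fisher's exact test. The tablet count has no named analysis, although the generic tests for continuous secondary outcomes in 9.4.2 and 9.4.5 could cover it.

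**Medication before the POD1 score.** Section 4.1 has investigators check pain medication use first; if any was given, "the questionnaire will be administered at least 1.5 hours after the patient has received the pain medication". The Schedule of Activities (1.3) marks "Concomitant medication review" at Visit 3. Section 10.1.9.1 has concomitant medications entered in the study database. No endpoint or analysis in section 9 uses this information, and 9.4.9 plans no exploratory analyses.

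**The equivalence rule.** Section 9.4.2 states: "A 95%, two-tailed confidence interval for the difference of mean pain scores between the two arms will be constructed". Equivalence of pain scores is concluded if both limits lie within ±1.

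**The concern.** There are two linked gaps.

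First, the endpoint is narrower than the objective. A tablet count misses any narcotic given by another route. It also treats in-hospital or additionally requested products as interchangeable with the discharge supply. The yes/no variable in 9.4.3 is a different quantity: it concerns requests beyond the discharge supply and carries no information about the hours before the POD1 score.

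Second, pain scores taken after analgesia reflect both the pain and its treatment. If one timing leaves more pain and those patients take more opioid, the scores can converge while opioid use diverges. The 1.5-hour wait governs the interval since the last dose, not the cumulative dose. Section 9.4.3 itself treats extra pain relief as an indicator of pain, and section 2.1 lists lower narcotic use among the aims. A reader told that the scores are equivalent would want to know whether opioid use up to that point was similar, and the plan produces no such result.

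**Working it through.** **1. Inputs.** From 9.2: "the expected mean difference of pain levels between the two groups is 1 likert point"; "Standard deviation (std) = 2"; alpha 0.05; power 0.8; equal allocation; 64 per arm. From 9.4.2: the 95% interval must lie within ±1.

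**2. The plan's own figure.** Normal approximation: n = 2 × (1.96 + 0.842)² × 2² / 1² ≈ 62.8, so 63 per arm. The exact two-sample t calculation gives 63.77, so 64 per arm, with power 0.801. The stated 64 reproduces, and nothing here alters the sample size.

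**3. What the equivalence rule requires.**
- Standard error = 2 × √(2/64) = 0.354.
- Expected half-width = t(0.975, 126 df) × 0.354 = 1.979 × 0.354 = 0.700.
- The interval fits inside ±1 only if the observed difference is within 1 − 0.700 = 0.300 of zero.

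For an expected difference d in the recorded scores, P(equivalence) ≈ Φ((0.300 − d)/0.354) − Φ((−0.300 − d)/0.354).

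**4. Illustration.** Suppose the true difference under equal opioid use is 1 point and extra analgesia in the worse arm removes part of it. The offset is an assumption; no figure for it is in the documents.

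| Assumed offset | Expected recorded difference | Φ terms | P(equivalence) | P(t-test rejects) |
|---|---|---|---|---|
| 0% | 1.0 | Φ(−1.98) − Φ(−3.68) | 0.024 | 0.80 |
| 50% | 0.5 | Φ(−0.565) − Φ(−2.26) | 0.274 | 0.29 |
| 100% | 0 | Φ(0.849) − Φ(−0.849) | 0.604 | 0.05 |

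A simulation of 1,000,000 trials with the SD estimated in each gives equivalence probabilities of 0.025, 0.276 and 0.603; the rejection probabilities are from the same simulation. Offsets of 25% and 75% give equivalence probabilities of 0.10 and 0.50.

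These probabilities are indexed by the expected difference, not the observed one. An observed difference of 0.5 with this half-width would give limits of −0.2 and 1.2 and would fail the rule.

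**5. The definitions side by side.**

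| Section | Narcotic outcome | Type |
|---|---|---|
| 1.1 | Total use over two weeks | Amount, unit not given |
| 3 | Number of tablets over two weeks | Count |
| 9.1 | Need for additional narcotic | Type not given |
| 9.4.3 | Request for additional narcotic | Yes/no |

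Two patients who use 0 and 12 of the supplied pills are identical under 9.4.3 and differ by 12 under section 3. Neither definition covers non-tablet narcotic or isolates the period before the POD1 score.

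**The case against.** Several counter-arguments have force.

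- **In-hospital dosing may be largely fixed.** Section 6.5 describes a standardised regimen ordered under an enhanced recovery protocol, and 6.5.1 marks rescue medicine as not applicable. Dosing by need is stated only for the discharge pills. A reader might infer that hospital analgesia is as-needed and that masking will occur. The conditional wording about prior medication in 4.1 is compatible with that but does not establish it. What stands is that unequal use is possible and would go unreported.
- **Early use is not wholly lost.** The diary is daily and starts at surgery, so tablets taken on the first days can be entered. Section 8.4.4 mentions a POD1 phone call, so some patients may already be at home with the diary. The gap is in non-tablet doses and in the analysis, not a complete absence of early data.
- **Tablet strength is partly standardised.** Every patient is discharged with the same standard supply, so the dose-unit problem arises mainly for in-hospital and additionally requested products.
- **Equivalence of scores under usual analgesia is a legitimate question.** Section 9.4.2 concludes about pain scores, not about interchangeability of the two timings in every respect. A reader might infer that equivalence should require similar opioid use as well. The documents do not support that: they give no opioid margin or SD, the trial is sized only for pain, and the pain rule alone passes about 60% of the time when the scores truly do not differ. A non-significant opioid difference would not show similarity either.

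The unnamed covariates in the supporting ANCOVA of 9.4.2 do not close the gap. Adjusting for opioid use, which is measured after randomisation, is not a comparison of it between arms.

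**Conclusion.** The point holds as a gap in endpoint content and reporting. The tablet count does not capture total narcotic use; sections 3 and 9.1/9.4.3 disagree on the outcome; and opioid use up to the primary score is not compared although medication is reviewed at that time. Similar pain scores could therefore coexist with unequal opioid use.

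The size is unknown, because the documents give no in-hospital drugs, routes or doses. The rise from about 2% to 27-60% rests on a true 1-point difference, SD 2, 64 per arm and an assumed offset of 50-100%. It shows how sensitive the rule is and is not a predicted error rate; the 60% is simply the pass rate whenever expected scores are equal. If all in-hospital narcotic were given as tablets, the conflict of definitions, the missing comparison before the score and the narrower dose-unit problem would remain.

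**What to change.** 1. Define the narcotic endpoint as total opioid dose in oral morphine equivalents from end of surgery to the two-week visit, taken from the medication record in hospital and the diary after discharge. Have the diary record product and strength, and fix the conversion table before analysis.
2. Reconcile sections 1.1, 3, 9.1 and 9.4.3, name the test for the total dose, and keep the yes/no request as a separate outcome.
3. Add a between-arm estimate with 95% confidence interval of opioid dose from end of surgery to the POD1 score, using the diary for any patient already at home. Class it as secondary or supportive and report it beside the primary result, for use in interpreting any equivalence conclusion. Do not use it as an adjustment covariate or as a second condition for declaring equivalence.

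Cost: abstraction of doses from charts already reviewed on POD1, a conversion table, slightly more diary detail and one more secondary comparison. Treatment and sample size are unchanged.
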